6.4. Handling of Missing Data and Dropouts

All data analyses will be based on the observed data. Missing data due to lost to follow-ups will not be imputed. For study subjects included in the primary analysis dataset who drop out or withdraw from the study, data collected before the occurrence of dropout or withdrawal will be included in analysis.

This document is electronically controlled. Printed copies are considered uncontrolled.

Confidential

6.5. Adjustments for Multiple Comparisons

The two-sided 95% CI will be conducted to test hypothesis for primary and the first secondary objective. For changes from the baseline, paired t-test will be performed to test whether the changes are statistically significant. No adjustments for multiple comparisons will be carried out.

6.6. Demographic and Other Baseline Characteristics

Demographic and other baseline information such as general history, comorbidities, musculoskeletal history, spine surgical history, medication, work status and indication for surgery will be summarized descriptively. In the indication for surgery, instead of summarizing measurements of length of body and slip in millimeter, the percentage of slip or grade/type of spondylolisthesis, and disc relative height for adjacent levels will be summarized due to zooming effect from x-ray and MRI. Continuous variables will be summarized using mean, standard deviation, median, minimum and maximum and categorical variables will be summarized using frequency and percentage tables.

Baseline information will be summarized for both all DDD patients and subgroup datasets defined in section 6.1.3 and/or per surgical procedure (ALIF, OLIF, DLIF, PLIF, TLIF, MIDLF) and per anterolateral and posterior groups.

6.7. Treatment Characteristics

Surgical procedure data include:

1. Duration of the surgery (minutes)
2. Estimated blood loss (ml) and transfusion
3. Total fluoroscopy time (seconds)
4. Levels treated
5. Procedure information (type of approach, access system, decompression, cage/interbody, anterior plate(s), posterior fixation technique, bonegraft and substitutes)

Continuous variables will be summarized using mean, standard deviation, median, minimum and maximum while categorical variables will be summarized using frequency tables.

Concomitant medications including nonopioid analgesics, opioid analgesics and other medications will also be summarized at each visit descriptively.

6.8. Interim Analyses

In this study, in addition to final report, an interim report when all subjects reach 3-month visit is anticipated. The methodology described in section 6.2 will be used for the interim analyses. The cumulative event rate for secondary surgery at index levels or adjacent levels and AEs up to cut-off date of interim analyses will be conducted by time-to-event analysis (life table method).

6.9. Evaluation of Objectives

All analyses will be performed based on the scheduled visits. A sensitivity analysis on primary endpoint will be performed as well. In the sensitivity analysis, the visits are defined based on the analysis visit window. In the case that two or more observations fall inside the same visit window, the observation which is closer to the nominal visit date will be analyzed.

The analysis visit windows are defined in Table 1, which is deviated from the scheduled visits defined in the CIP.

For subjects who have additional surgical procedures at the index levels or have implanted device explanted, since these additional surgical procedures are considered to have interfered with clinical outcomes of intended treatments, the last observation taken before the first additional surgical procedures will be carried forward for all future evaluation periods for clinical endpoints and radiographic endpoints.

Table 1: Analysis Visit Window

Study Visit	Analysis Visit Window
Surgery	Day 0
Postop (Day 1 to 2-Week)	Day 1 to 14
4-Week	(>2 to 6 weeks): Day 15 to 42
3-Month	(>6 weeks to 6 months): Day 43 to 182
1-Year	(>6 to 18 months): Day 183 to 547
2-Year	(>18 to 30 months): Day 548 to 912
3-Year	(>30 to 42 months): Day 913 to 1277
4-Year	(>42 to 54 months): Day 1278 to 1642
5-Year	(>54 months): Day 1643 and beyond

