**Table 3: Description of Procedures and Assessments at different time intervals**

Pre-operative visit (Baseline):	

• Written Patient Informed Consent /Data Release Form

• Demographic data

• Medical history

• Work status

• Pain medication

--------------------------------------------	------------------------------------------------------------------------------------------------------------------------------------------------------------------------------------------------------------

	
 
• VAS Back and leg pain
 
• ODI
 
• EQ-5D
 
• Neurological status
 
• AP & Lateral Radiographic Evaluation
 
• Imaging (MRI and/or CT Scan)
 
• Sagittal balance (in those sites where this assessment is Standard of care)
 
• DN4 for back and DN4 for leg**
 

Surgical procedure:	
 
• Surgery procedure data
 
• Surgery time
 
• Blood loss and Transfusion
 
• Device Models
 
• Adverse Events
 

Hospital stay and discharge: (Surgery = Day 0)	
 
• Length of hospital stay (in days)
 
• VAS Back and leg pain (at Day 2, the day the patient is considered recovered from the surgery(=SRD) and/or Day of discharge)
 
• Time in days to first ambulation
 
• Surgery Recovery Day
 
• Record pain medication
 
• Adverse Events
 

Postoperative assessment at 4w (<math>\pm 2w</math>): 3m (-1.5/+3m)	
 
• VAS Back and leg pain
 
• ODI
 
• EQ-5D
 
• Neurological Status
 
• Work Status and rehabilitation program
 
• Pain medication
 
• Adverse Events
 
• Sagittal balance (in those sites where this assessment is standard of care)
 
• DN4 for back and DN4 for leg (at 3m only)**
 

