#### **E.5 Post Procedure to Discharge**

All subjects will be assessed until discharge. Assessments are described in Table 2 .

Day 2 after the procedure, at SRD and at discharge following assessments will be collected:

Pain medication, VAS Leg and Back pain intensity scores, hospital data and AEs.

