## E.7 Data collection requirements

Table 2 summarizes what data will be collected prospectively within this study.

After the surgery, regular patient follow up visits will be done to complete the Quality of Life questionnaires and to assess work status, and rehabilitation program.

While a hospital visit is required for the 3 months (-1.5/+3 month) and 1 year ( $\pm$  6 month) follow up; the Postoperative follow-up assessment at 4 weeks ( $\pm$  2 weeks), 2 years ( $\pm$  6 months), 3 years ( $\pm$  6 months), 4 years, ( $\pm$  6 months), and 5 years ( $\pm$  6 months) can either be done through a patient visit at the hospital or by means of a phone call done by the investigator and/or authorized designee.

The ODI outcome measurements are preferably done by site staff different than the surgeon who operated the patient. Training will be provided to the site to collect the ODI outcome measurements in an independent way without influencing the patients.

Imaging is critical for assessing fusion. At 1 year follow up, each site should at least perform a CT scan or X-Rays per patient to assess fusion. If no fusion is observed, 1 year after the surgery, further fusion follow up assessment will be at the discretion of the investigator and the investigator will have the opportunity to enter this data in the CRF.

Sagittal Balance will only be collected in those sites where it is standard of care to assess the sagittal balance of the patient.

Calibration and maintenance of imaging equipment should be done according to the instructions of the manufacturer of the equipment and according to local protocols per Institution's standards.

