6.9.2.2.2. Neurological success

Neurological status is based on four sections: motor, sensory, reflexes, and straight leg raising. Each of the sections is comprised of a number of elements.

6.9.2.2.2.1 Motor Function

For the motor function, the assessments are listed in ascending order of improving as indicated below:

0 = Total Paralysis

1 = Palpable or Visible Contraction

2 = Active Movement, Gravity Eliminated

This document is electronically controlled. Printed copies are considered uncontrolled.

Confidential

3 = Active Movement, Against Gravity

4 = Active Movement, Against Some Resistance

5 = Active Movement, Against Full Resistance (full strength) (Normal)

For the time period evaluated, for each of elements, if the score increases from baseline, the subject is considered "improved"; if the score remains the same as baseline, the subject is considered "maintained"; if the score decreases from the baseline, the subject is considered "deteriorated". In the situation where the score at baseline is 0 (Total Paralysis) and a postoperative visit is missing, or the score at baseline is missing and at a postoperative visit is 5 (Normal), the subject is conservatively considered as "maintained". For overall motor status, if at least one element has the status of "improved" and the rest are "maintained", then the overall motor status is considered "improved"; if all elements have the status of "maintained", then the overall motor status is "maintained"; if at least one element has the status of "deteriorated", then the overall motor status is "deteriorated."

6.9.2.2.2.2 Sensory function (Light Touch or Pin Prick L1 to S1)

For the sensory function, the assessments include absent, impaired and present (normal) which are listed in ascending order of improving. Let absent be 0, impaired be 1 and normal be 2. The same logic outlined in the motor function section will be used to first determine the change status of each element from the baseline and then the overall sensory status from the baseline. For each element, in the situation where the score at baseline is 0 (Absent) and a postoperative visit is missing, or the score at baseline is missing and at a postoperative visit is 2 (Normal), the subject is conservatively considered as "maintained".

6.9.2.2.2.3 Reflexes

For the reflexes, the assessments are listed as indicated below:

0 = Absent or Trace

1 = Hyper-reflexic

2 = Normal

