For each element, a change from 0 (Absent or Trace) to 2 (Normal) or 1 (Hyper-reflexic) to 2 (Normal) is considered improved while the other way around is considered deteriorated. No change is considered maintained. Any change from 0 (Absent or Trace) to 1 (Hyper-reflexic) is considered "diminished to hyperactive" while the other way around is considered "hyperactive to diminished". In the situation where the score at baseline is missing and at a postoperative visit is 2 (Normal), the subject is conservatively considered as "maintained". If none of element has the situation of "diminished to hyperactive" or "hyperactive to diminished", an overall evaluation of reflex will be summarized using the same logic outlined in the motor function section. Otherwise, there will be no overall evaluation.

6.9.2.2.2.4 Straight leg raise

For the straight leg raise, the assessments include positive and negative (normal). Let positive be 0 and negative be 1. The same logic outlined in the motor function section will be used to first determine the

This document is electronically controlled. Printed copies are considered uncontrolled.

Confidential

change status of each element from the baseline and then the overall straight leg raise status from the baseline. For each element, in the situation where the score at baseline is 0 (Positive) and a postoperative visit is missing, or the score at baseline is missing and at a postoperative visit is 1 (Negative), the subject is conservatively considered as "maintained".

Overall neurological success will be defined as maintenance or improvement in all sections (motor, sensory, reflex, and straight leg raising) for the time period evaluated. In order for a section to be considered a success, each element in the section must remain the same or improved from the time of the baseline evaluation to the time period evaluated. If at least one section is deteriorated, the overall neurological success will be defined as failure.

Summary statistics (frequencies) will be presented for status of each section and overall neurological success at each follow-up.

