6.9.2.2.3. Fusion success

Fusion will be assessed at 1 year, preferably by collecting a CT-scan, alternatively fusion may also be collected through X-Rays. If no fusion observed during the first fusion assessment, further fusion assessment(s) will be at the discretion of the investigator. The surgeon or hospital radiologist will determine fusion. Time-to-event analysis will be conducted for fusion success. The fusion success rate will be summarized at 1, 2, 3, 4 and 5-year follow-up, if applicable. If a subject shows fusion success at early timepoints and non-fusion at a later timepoint, the fusion status at all earlier points should be considered non-fusion. For 2-level subjects, fusion success will be defined as achieving fusion at both treated levels. In addition to the time-to-event analysis, the last evaluation for fusion will be summarized.

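### A preoperative neurological baseline can be carried forward as success to 5 years when index-level re-operation precedes the first postoperative examination, and the SAP does not say how early revisions enter the fusion rate

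*SAP*

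**What the plan says.** - **Carry-forward rule.** SAP 6.9 covers patients who have additional surgery at the index level or an implant removed. For them, "the last observation taken before the first additional surgical procedures will be carried forward for all future evaluation periods for clinical endpoints and radiographic endpoints". The stated reason is that such surgery interferes with the outcome of the intended treatment. No minimum is set on when the carried observation was made.
- **In-hospital assessments.** Protocol E.5 lists what is collected on Day 2, at the surgery recovery day and at discharge: "Pain medication, VAS Leg and Back pain intensity scores, hospital data and AEs". Neurological status is not among them.
- **First postoperative neurological status.** Protocol Table 3 lists it under "Postoperative assessment at 4w". Protocol E.7 says that the 4-week contact, like those at 2 to 5 years, "can either be done through a patient visit at the hospital or by means of a phone call". A hospital visit is required only at 3 months and 1 year.
- **Scoring.** In SAP 6.9.2.2.2, "if the score remains the same as baseline, the subject is considered" 'maintained'. Then: "Overall neurological success will be defined as maintenance or improvement in all sections".
- **Fusion.** SAP 6.9.2.2.3: "Fusion will be assessed at 1 year, preferably by collecting a CT-scan". The fusion rate is summarised by year, by a time-to-event analysis and by the last evaluation.
- **Missing data.** SAP 6.4 bases analyses on observed data and does not impute values missing through loss to follow-up.

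**The concern.** The rule takes for granted that a postoperative observation exists before the re-operation. For neurological status there is a period after surgery in which none is scheduled. A patient who wakes with a new deficit and is revised in that period has only a preoperative examination on file. Carrying it forward records no change from the preoperative state at a time when the patient may have been worse, and it replaces examinations made after the revision.

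The patients concerned have had one of the less favourable courses after the index operation, so scoring them as successes moves the rate the wrong way. The period is not empty of plausible causes: the protocol's own list of related events (E.9.1.1) includes nerve root injury, dural tear, cage migration and screw pullout.

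For fusion the difficulty is of another kind. Before the first image there is no fusion reading to carry, and the SAP does not say what happens next.

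**Working it through.** The plan states neither an early re-operation rate nor an expected neurological success rate, so it has no figure of its own to reproduce here. The check traces the rule through the schedule and then bounds its effect.

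**Tracing the neurological rule**

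1. Baseline: neurological status is scheduled (protocol Tables 3 and 4).
2. Day 2, surgery recovery day, discharge: not scheduled (protocol E.5, Tables 3 and 4).
3. 4 weeks (± 2 weeks): first scheduled examination. If this contact is by phone, strength, reflexes and straight leg raising cannot be examined. The next required hospital visit is at 3 months, with a window from 3 − 1.5 = 1.5 months to 3 + 3 = 6 months.
4. Re-operation inside this gap: the only earlier observation is baseline. SAP 6.9 assigns it to 4 weeks, 3 months and years 1 to 5, seven follow-ups in all.
5. The change for each recorded element is baseline minus baseline = 0, hence 'maintained'. Every section is then maintained, and the patient is an overall success at all seven.
6. A later examination showing deterioration is overridden by the carried value.

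**Size for neurological success**

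Inputs: N = 350 (SAP 5). The share re-operated before the first postoperative examination is assumed at 1%, 2%, 3% and 5%, giving k patients after rounding. Success in the others is assumed to be 90%, and all 350 are taken as evaluable.

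- Rate under the literal rule: [0.90 × (350 − k) + k] / 350
- Rate if all k are failures: 0.90 × (350 − k) / 350
- Difference: k / 350, which does not depend on the 90%

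| Assumed share | k | Literal rule | All k failures | Difference (points) |
|---|---|---|---|---|
| 1% | 4 | 90.1% | 89.0% | 1.1 |
| 2% | 7 | 90.2% | 88.2% | 2.0 |
| 3% | 10 | 90.3% | 87.4% | 2.9 |
| 5% | 18 | 90.5% | 85.4% | 5.1 |

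These differences are upper bounds. At any visit the overstatement is the number of the k patients who are truly worse than baseline at that visit, divided by 350. With 2% re-operated and half of them worse, it is 3.5 / 350 = 1.0 point, and it shrinks at later visits if deficits resolve.

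**Fusion**

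Fusion is first assessed at 1 year. The visit window is ± 6 months (protocol E.6), and the analysis window opens on Day 183 (SAP 6.9, Table 1). For a revision before that image, the carry-forward rule has nothing to carry. Two readings remain: the later image is used as observed data, or the patient has no fusion result.

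To show how far handling could matter, take the 94.8% fusion rate that protocol A.1.3 cites for minimally invasive TLIF, and assume that 2%, 5% or 10% (7, 18 or 35 patients) are revised before the first image. Leaving them out gives 94.8% of 343, 332 or 315. Counting all of them as not fused gives 0.948 × 343/350 = 92.9%, 0.948 × 332/350 = 89.9% and 0.948 × 315/350 = 85.3%. These are the ends of a sensitivity range, not an estimate of bias.

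**The case against.** **Baseline may not count.** The SAP never says that a preoperative value qualifies as the last observation. If only postoperative values are carried, these patients are missing for neurological success, not successes. This stands as an alternative reading, but the text does not state it, and on neither reading does the plan count a deteriorated patient as a failure. Protocol E.3 also ties baseline neurological documentation to the presence of an abnormality, so some elements may have no baseline record and could not be scored as maintained. This too stands, and it lowers the number affected.

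**Fusion.** A reader might infer that early-revised patients drop out of the fusion rate. The documents do not establish that. With nothing to carry, the observed-data principle in SAP 6.4 allows the later image to be used. The time-to-event and last-evaluation summaries give further routes in, and the X-ray criterion in protocol B.1.3 already requires intact instrumentation. What remains is an unstated rule, not a demonstrated bias.

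**Comparison of approaches.** A reader might also infer that the plan tilts a comparison towards the approach with more early revisions. Neurological and fusion success carry no hypothesis test (protocol B.4, SAP 6.2). They are tabulated by approach, so a distortion could appear in the tables, but no formal conclusion rests on them.

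**Events are reported elsewhere.** Re-operations have a 5-year life table (SAP 6.9.2.2.4), all adverse events are summarised (SAP 6.10), and a new neurological abnormality is itself an adverse event (protocol E.6). The events are therefore not hidden. This does not correct the success rate.

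**Using examinations after re-operation** runs against the SAP's reason for carrying values forward, and treats a patient revised just before the first examination differently from one revised just after. That is a fair cost, and the reason to pair the change with a sensitivity analysis.

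**Conclusion.** The point holds for neurological success on the literal wording of SAP 6.9: a patient re-operated at the index level before the first postoperative examination is scored a success to 5 years from a preoperative value. The descriptive rate is biased upward by at most about 1–5 percentage points if 1–5% of 350 patients are affected and all had failed, and by about 1 point if 2% are affected and half have a deficit. Every one of these rates is an assumption, because the documents give none. The result also assumes that baseline counts as an observation and was recorded.

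For fusion, the finding is only that handling of a revision or explant before the first image is not stated. The primary ODI conclusion is not affected by this point.

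**What to change.** In SAP 6.9:

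- **Neurological success.** State that a preoperative value is never carried forward. When an index-level re-operation or explant precedes the first postoperative examination, use the later examinations as observed. Add a sensitivity analysis counting these patients as failures, and list them by approach.
- **Fusion.** State that a patient revised or explanted before the first image stays in the denominator, with the later observed image used where one exists. Add a sensitivity analysis counting these patients as not fused.

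The cost is SAP wording, a little more analysis work and possibly slightly lower reported success rates. Re-operations, later visits and later images are already collected, so no visit or assessment is added. Because the 2- to 5-year contacts may be by phone, some later examinations may be missing. The listing should show which visits were examined.

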#### Fusion

From the surgical point of view, fusion is the main target of performing the procedure.

Fusion will be assessed at 1 year, preferably by collecting a CT-scan, alternatively fusion may also be collected thru X-Rays. If no fusion is observed during the first fusion assessment further fusion assessment(s) will be at the discretion of the investigator. The criterion for fusion when assessed thru a CT-scan is bony bridging and when assessed thru X-Rays the criteria are bony bridging, no motion (<4°) in Flexion/Extension views and integrity of

instrumentation (implanted devices). The surgeon or hospital radiologist will determine fusion. Fusion success rate will be summarized at 1, 2, 3, 4, 5 -year follow-up. If a subject shows fusion success at early timepoints and non-fusion at a later timepoint, the fusion status at all earlier points should be considered as non-fusion. For 2-level subjects, fusion success will be defined as achieving fusion at both treated levels.

Proportion of patients needing a second surgery at the index and/or adjacent level(s) (reoperation rates) throughout the study

When a patient requires additional surgery at the index and/or adjacent level(s), it can be an indicator of insufficient outcomes of the initial surgery. As such, this is a reflection of the efficiency of the initial surgery and therefore is of great clinical value to the surgical community and through that to the patients. Due to the progressive nature of the degenerative lumbar spine, additional surgeries at the index and/or adjacent level might be required after the initial surgery. To ensure all safety and economic values are collected, the revision surgeries and their complication types and rates will be assessed during the study as assessed by the surgeons.

In case the investigator or hospital becomes aware of a second surgery at the index and/or adjacent level in another hospital, this should also be documented in the AE eCRF.

Document Adverse Events occurrence throughout the study

The study is designed to observe and document events related to clinical safety and performance of the devices according to approved instructions for use. During the follow up period (up to 5 years), the occurrence of all AEs will be monitored, registered and analyzed. To safeguard the safety of the clinical study subjects, all AEs will be collected even those that may not be directly related to the surgery.

Time in days needed for first ambulation

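### If the last fusion reading before an index-level re-operation or explant is 'fused', SAP 6.9 carries it to year 5 and the rule that later non-fusion overturns earlier fusion cannot act

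*SAP*

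**What the plan says.** **Carry-forward.** SAP 6.9 (Evaluation of Objectives) applies "For subjects who have additional surgical procedures at the index levels or have implanted device explanted". For these patients the last value observed before the first such surgery "will be carried forward for all future evaluation periods for clinical endpoints and radiographic endpoints". The stated reason is that the extra surgery interferes with the outcome of the intended treatment. There is no exception by reason for revision, and none for fusion.

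**Reversal.** SAP 6.9.2.2.3 covers the patient who is fused early and has "non-fusion at a later timepoint, the fusion status at all earlier points should be considered non-fusion". CIP B.1.3 (Fusion) and G.1.2 state the same rule.

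**Imaging.** Fusion is read at 1 year. After that, CIP B.1.3 says: "If no fusion is observed during the first fusion assessment further fusion assessment(s) will be at the discretion of the investigator". Neither document requires another fusion reading once a patient is fused. CIP E.7 allows the visits at years 2 to 5 to take place by phone.

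**Criteria.** Under CIP B.1.3, CT fusion means bony bridging. X-ray fusion means bony bridging, motion below 4 degrees and intact instrumentation.

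**Imputation.** CIP G.1 restricts analyses to observed data and contains no carry-forward. SAP 6.12 marks changes to the planned analysis as not applicable.

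**The concern.** The two SAP rules can give opposite answers for the same patient. The reversal rule exists so that a fusion that later proves wrong or lost is not reported as a success. A patient read as fused at 1 year may never be imaged for fusion again, so a revision is one of the main occasions on which non-fusion would come to light. From that point, SAP 6.9 fixes the earlier value in place.

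At stake are the fusion rates at years 1 to 5 and the time-to-event analysis, which would keep a fusion event at year 1. CIP B.1.3 describes fusion as the surgeon's main aim in operating. There is also a reproducibility problem: SAP 7 relies on independent double programming, and two programmers could each follow the text and derive different statuses.

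**Working it through.** The plan states no figure on this point, so there is none to reproduce. The check applies the two rules to patient paths and then does simple arithmetic on the rate.

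**Step 1: patient paths.** Each patient is fused at year 1 and revised at the index level at 2.5 years.

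| Path | Readings on record | After carry-forward | After the reversal rule |
|---|---|---|---|
| A | Year 1 fused, year 3 not fused | Years 3, 4 and 5 fused | No non-fusion left to act on; year 1 and years 3–5 stay fused |
| B | Year 1 fused, year 2 not fused | Years 3, 4 and 5 not fused | Year 1 reset; not fused throughout |
| C | As A, without carry-forward | Not applied | Year 3 non-fusion resets year 1 to not fused |

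A and C use the same data and end in opposite statuses, so the carry-forward alone makes the difference. B shows that the rule does not fix the 1-year value as such. It carries whatever was last observed before surgery, and a recorded non-fusion passes through and triggers the reset.

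**Step 2: which path is likely.** Path B needs a non-fusion reading between year 1 and the revision. None is scheduled for a patient already read as fused. A diagnostic image might supply one, but SAP 6.9 also says "All analyses will be performed based on the scheduled visits", and the SAP does not say whether an image taken between visits counts.

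**Step 3: size.** With k affected patients among N, the overstatement is 100 × k/N points. Inputs:
- N = 350, the planned enrolment in SAP section 3.
- A reported rate of 94.8%, the MIS TLIF literature figure in CIP A.1.3. It is an illustration, not a design assumption.
- k is assumed, to span roughly 1% to 5% of patients.

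| k | 100 × k/350 | Rate if these patients count as not fused |
|---|---|---|
| 4 | 1.1 | 93.7% |
| 7 | 2.0 | 92.8% |
| 10 | 2.9 | 91.9% |
| 18 | 5.1 | 89.7% |

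If fewer than 350 patients have a fusion reading, each affected patient weighs more.

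**The case against.** The best defence is that the carry-forward is deliberate and works in both directions. An image after revision shows the revised construct. The same rule stops a patient who was not fused, then revised and then fused, from counting as a success of the index procedure. That stands, and it argues against exempting fusion from carry-forward altogether. It does not justify overwriting non-fusion. Non-union already present when the patient is re-operated is an outcome of the index surgery, not interference with it. A non-fusion image after revision is less clear evidence about the index fusion, but the reversal rule draws no such distinction.

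Four stronger readings are tempting, and the documents do not support them.

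- *Every patient fused at 1 year and later revised for non-union stays fused.* Path B shows otherwise.
- *Revision for failed hardware is fusion failure.* Under the preferred method, CT, a bridged level with a broken rod is still fused. Only the X-ray criteria include intact instrumentation.
- *The summary of the last fusion evaluation is overstated too.* SAP 6.9.2.2.3 does not say whether that evaluation precedes or follows revision.
- *The size can be taken from the 20% five-year re-operation figure in CIP A.1.4.* That figure concerns open fusion and is not limited to the index level. It may also apply only to the 18% with complications, which would give 0.18 × 0.20 = 3.6%.

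Further readings are also not excluded. The CIP table describing procedures and assessments by time interval lists fusion status at every annual visit, and CIP E.6 provides follow-up X-rays for sagittal balance where these are standard of care. They are simply not required to assess fusion again. Finally, each revision is still reported in the secondary-surgery life table (SAP 6.9.2.2.4), so it is not hidden from the reader.

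**Conclusion.** The conflict is real but conditional. It acts when the last reading before an index-level re-operation or explant is fused, and it then produces a wrong status under a literal reading of the SAP. This is a stated rule with a wrong result, not merely missing detail.

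The documents give no rate of revision after a fused 1-year reading, so the range of about 1 to 5 points in the working rests wholly on assumed shares. A difference in bias between the anterolateral and posterior groups is possible if their revision rates differ, but nothing in the documents shows that they do.

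The consequence is limited to a secondary endpoint without a hypothesis test (CIP B.4). The SAP should be corrected before fusion is analysed.

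**What to change.** In SAP 6.9 and 6.9.2.2.3, state for fusion that:

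1. Carry-forward may not overwrite a non-fusion reading, so the reversal rule takes precedence. Fusion first seen after an index-level revision is not credited to the index procedure.
2. Diagnostic imaging that shows non-fusion before the revision, and non-union documented at the revision, count as non-fusion readings.
3. A sensitivity analysis counts every index-level re-operation or explant as fusion failure.

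Instrumentation failure alone should not be reclassified as non-fusion in the main analysis, because that would change the CIP's CT definition. The SAP should also record and justify the carry-forward as a departure from the observed-data rule in CIP G.1, since CIP G.1.3 asks for deviations to be documented.

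The cost is SAP wording, one extra derivation and possibly slightly lower reported fusion rates. No added imaging is needed. One check is required first: the CIP routes second surgeries at the index or adjacent level to the AE eCRF, but neither document shows that the form records the reason for the revision or the finding at surgery.
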